11.3. Accrual estimates

In our clinic on average 30 patients per month are seen with lung nodules. Of these patients around 50% have truly indeterminate lung nodules for which clinical management is uncertain. We estimate that about 20% of the eligible candidates will consent to participate in the study, leading to an accrual of circa 3 patients per month. We expect to be able to complete the study (50 patients) within 3 years.

After the first 2.5 years of the study, we will assess the long-term follow up rate and add

¹⁸F-FSPG PET/CT and Integrated Biomarkers for Early Lung Cancer Detection in Patients with Indeterminate Pulmonary Nodules

additional patients if accrual is not sufficient. We will not do an interim statistical analysis.

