2.6. Study Design

120 patients with indeterminate lung nodules will be enrolled in the study at Stanford. Blood and nasal brushings will be collected once. The samples from these 120 patients will be part of a bigger cohort of over 900 patients for collaborative data analysis.

All samples will be de-identified before shipment or other data sharing with collaborators takes place. An additional 70 patients who may or may not have smoking history will be imaged at Stanford and analyzed with the other 50 patients enrolled at Stanford.

All 120 patients will be imaged once by ¹⁸F-FSPG PET/CT as part of this open-label, nonrandomized, single-dose explorative study and once by ¹⁸F-FDG PET/CT. PET/CT imaging will be scheduled > 24 hours apart to allow for imaging agent washout, and not more than two weeks apart to allow for optimal image comparison.

Clinical diagnosis (cancer / benign disease) is based on 1) histopathology of biopsy/surgical specimen or 2) surveillance by CT scans for a period of 2 years to confirm that there is no

¹⁸F-FSPG PET/CT and Integrated Biomarkers for Early Lung Cancer Detection in Patients with Indeterminate Pulmonary Nodules

growth of the nodule. All patients without histopathological diagnosis will undergo CT surveillance for a 2-year period by clinical standards.

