V. Statement of Eligibility

By signing this form of this trial I verify that this subject is: eligible / ineligible for participation in the study. This study is approved by the Stanford Cancer Institute Scientific Review Committee, the IRB of record, and has finalized financial and contractual agreements as required by Stanford School of Medicine's Research Management Group.

Study Coordinator printed name:	Date:
Signature:	
Investigator printed name:	Date:
Signature:	
Triple-check reviewer printed name:	Date:
Signature:	

¹⁸F-FSPG PET/CT and Integrated Biomarkers for Early Lung Cancer Detection in Patients with Indeterminate Pulmonary Nodules

Eligibility Checklist (Group 2: Smokers and Non-Smokers)

I. Protocol Information

Protocol Title:	18F-FSPG PET/CT and Integrated Biomarkers for Early Lung Cancer Detection in Patients with Indeterminate Pulmonary Nodules
Group	Group 2: Smokers and non-smokers
eProtocol number: OnCore number:	IRB-46607 LUN0106
Principal Investigator:	[name] [name]

II. Subject Information

Subject name / Unique ID:	/	
Gender	 Male	 Female

III. Study Information

Inclusion Criteria

Prospective Participant Must MATCH ALL these Inclusion Criteria to be Eligible	Yes	No	Supporting Documentation *
1. Pulmonary nodule between the size of 7 to 30 mm. Subjects with multiple nodules may be eligible if the dominant nodule is 7 to 30 mm.			
2. ≥ 45 years old			
3. Documented informed consent			

Exclusion Criteria

Prospective Participants Must NOT Match ANY of These Exclusion Criteria	Yes	No	Supporting Documentation *
1. History or previous diagnosis of lung cancer			
2. Any other current or previous malignancy within the past 5 years other than exceptions as determined by the opinion of the treating MD and PI, which include: 
• Adequately treated basal cell or squamous cell skin cancer• Carcinoma in situ of cervix• Prostate cancer with stable PSA level for >3 years, or• Other neoplasm that, in the opinion of the treating MD and PI, will not interfere with study-specific endpoints			
3. Pregnant or nursing (per department of radiology policy)			

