3.2. Informed Consent Process

All participants must be provided a consent form describing the study with sufficient information for participants to make an informed decision regarding their participation. Participants must sign the IRB approved informed consent prior to participation in any study specific procedure. The participant must receive a copy of the signed and dated consent document. The original signed copy of the consent document must be retained in the medical record or research file.

Study Timeline

3.2.1. Primary Completion:

The study will reach primary completion 36 months from the time the study opens to accrual.

3.2.2. Study Completion:

The study will reach study completion 60 months from the time the study opens to accrual.

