10. MEASUREMENTS

10.1. Primary Outcome Measure (ClinicalTrials.gov)

The primary outcome is specificity of ¹⁸F-FSPG to discriminate between benign and malignant lung nodules, defined as the proportion of benign cases judged to be benign. With an expected 60 benign cases, an observed 90% specificity would have a 95% confidence interval of 79% to 96%. An observed specificity of 75% would have a confidence interval of 62-85%.

If a patient has multiple nodules, the per-patient assessment will be based on the dominant nodule only, defined as the largest nodule.

Outcome Title: ¹⁸F-FSPG specificity for malignant lung nodules.

Outcome Description: ¹⁸F-FSPG accumulation in lung nodules will be assessed. The observed FSPG specificity will be assessed against a fixed value of 75%.

Timeframe: Up to 5 years.

Safety Issue: No.

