11. STATISTICAL CONSIDERATIONS

11.1. Statistical Design and Data Analysis

Clinical diagnosis is based on 1) histopathology of biopsy/surgical specimen or 2) surveillance by CT scans for a period of 2 years to confirm that there is no growth of the nodule. Meta-analysis shows that ¹⁸F-FDG has a sensitivity and specificity of 89% and 75% respectively (16). We hypothesize that ¹⁸F-FSPG is more specific. With an expected 90% specificity for diagnosis with ¹⁸F-FSPG, a sample size of 60 will have 90% power at an alpha-level of 0.05 to demonstrate a significant increase in specificity from a fixed value of 75%.

Integrated predictions models:

Our biomarker discovery and validation will use samples from 930 patients in the intended use population collected prior to diagnosis; and subsample from all available cancer and non-cancer patients. Through our experience with the NCI Early Detection Research Network (EDRN), we have a detailed plan for biomarker discovery and validation, which is briefly summarized here.

¹⁸F-FSPG PET/CT and Integrated Biomarkers for Early Lung Cancer Detection in Patients with Indeterminate Pulmonary Nodules

Identification of candidate genes from nasal total RNA-seq data: We will initially select 20 to 40 candidate genes that significantly discriminate between cases (n = 100) and controls (n = 100). We will prioritize candidates to: 1) represent cancer-associated gene co-expression patterns, 2) genes whose expression is independent of clinical factors, and genes in significantly enriched functional categories.

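### Section 11.3 projects accrual for 50 patients, not the 120 planned, and the 36-month primary completion leaves no room for the two-year surveillance that classifies benign nodules

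*Combined protocol and SAP*

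**What the plan says.** Section 11.3 builds its rate from about 30 nodule patients seen per month, of whom around half are truly indeterminate and about 20% of those consent. It arrives at circa 3 per month and concludes: "We expect to be able to complete the study (50 patients) within 3 years". It adds a review of accrual and follow-up after 2.5 years, at which patients may be added.

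The sample for the primary outcome is larger. Section 2.6 says: "An additional 70 patients who may or may not have smoking history will be imaged at Stanford and analyzed with the other 50 patients". Section 11.2 bases the power statement on the resulting 120 patients, about 60 of them benign. Section 3.1 has a separate checklist for the added group, without the smoking requirement.

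On timing, section 3.2.1 says: "The study will reach primary completion 36 months from the time the study opens to accrual". Section 3.2.2 says: "The study will reach study completion 60 months from the time the study opens to accrual". Section 10.1 gives the primary outcome "Timeframe: Up to 5 years".

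On the reference standard, section 11.1 accepts histopathology or "surveillance by CT scans for a period of 2 years to confirm that there is no growth of the nodule", and section 2.6 adds: "All patients without histopathological diagnosis will undergo CT surveillance for a 2-year period by clinical standards". A rule to wait until every patient has two years of follow-up, a positive diagnosis or has died appears in section 11.1, within the text on the integrated prediction models.

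**The concern.** The accrual section supports fewer than half of the patients on whom the power statement rests, and no projection for 120 appears anywhere. The primary outcome is the proportion of benign patients judged benign, so its denominator is the group most likely to depend on two years of surveillance. A primary completion date 36 months after opening leaves that surveillance finished only for patients who enrolled in the first 12 months, unless it was already under way at enrolment.

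At stake is whether the planned 60 benign patients are all classified when specificity is calculated. If the sponsor waits, the stated date is missed. If the sponsor holds to the date, part of the denominator is unclassified. The missing part would not be random, because benign patients with histology are classified early and those under surveillance late.

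**Working it through.** **Inputs.** From 11.3: 30 patients per month, 50% indeterminate, 20% consent, 50 patients within 3 years, review at 2.5 years. From 2.6 and 11.2: 50 + 70 = 120 patients, about half benign. From 3.2: 36 and 60 months. From 2.6 and 11.1: 24 months of surveillance without histology.

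**The plan's own figure.** 30 × 0.50 × 0.20 = 3.0 per month, as stated. 50 / 3 = 16.7 months, so enrolling 50 within 3 years is consistent. The product contains no smoking restriction, so on the documents' own calculation admitting non-smokers does not raise it, and no separate rate is given for the 70.

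**Enrolment of 120.**
- 120 / 3 = 40 months.
- By month 36: 3 × 36 = 108 enrolled, 12 short.
- Rate needed for 120 by month 36: 120 / 36 = 3.33 per month, which is 3.33 / 15 = 22% consent instead of 20%.

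**Adding surveillance.** Let the lead be the months of surveillance already completed at enrolment. The last patient without histology is classified at month 120 / rate + 24 − lead.

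| Rate per month | Enrolment ends | Lead 0 | Lead 4 | Lead 12 | Lead 24 |
|---|---|---|---|---|---|
| 2.5 | 48 | 72 | 68 | 60 | 48 |
| 3 | 40 | 64 | 60 | 52 | 40 |
| 3.33 | 36 | 60 | 56 | 48 | 36 |

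These are upper bounds, because a patient with histology is classified sooner. Month 36 is reached only at 3.33 per month with a full 24-month lead. With no lead, having all 120 through surveillance by month 36 needs 120 / 12 = 10 per month, or 10 / 15 = 67% consent. Even the 50 patients of 11.3 would need up to 16.7 + 24 = 40.7 months.

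**What a calculation at month 36 would contain.** At 3 per month with no lead, 108 × 0.5 = 54 benign patients are enrolled, and (36 − 24) × 3 × 0.5 = 18 have completed surveillance. If a share h of benign patients has prompt histology, the number classified is 18 + h × (54 − 18). The last column is the exact binomial power for 90% against 75% at one-sided 0.05; the plan does not state sidedness.

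| h (illustrative) | Benign classified | Power |
|---|---|---|
| 0 | 18 | 45% |
| 25% | 27 | 48% |
| 50% | 36 | 71% |
| 100% | 54 | 83% |
| Plan | 60 | 93% |

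**The 2.5-year review.** Patients added in months 30 to 36 reach two years from enrolment in months 54 to 60: inside study completion, outside primary completion.

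**The case against.** The best defence is that 36 and 60 months differ by exactly the 24 months of surveillance, and that 60 months is five years. On that reading the sponsor means 36 months of accrual plus 24 of follow-up, and has only labelled the first date loosely. The three accrual inputs are approximate, so circa 3 could well be 3.33, and enrolment then ends on time. This largely stands. It means that 60 months and the 10.1 timeframe, which is only an upper bound, are not contradicted. It does not rescue 36 months as the primary completion of an outcome that needs two-year status, and it leaves the 50 in 11.3 uncorrected.

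It is also fair that no section schedules a specificity calculation at month 36, and that 11.3 rules out an interim analysis. The table for month 36 therefore shows what holding to the date would cost; it is not what the plan says will happen.

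A reader might infer more than the documents support:
- That 36 months is impossible on enrolment alone. It is not: the gap is 4 months and 12 patients at exactly 3 per month, within the looseness of the inputs.
- That the study must run to month 64. That is an upper bound, which requires late enrollees without histology and surveillance counted from enrolment.
- That the 2.5-year review is useless. It can still work within 60 months.
- That the waiting rule in 11.1 already governs specificity. It sits in the prediction-model text, and 10.1 does not refer to it.

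**Conclusion.** The concern holds in a limited form. Section 11.3 was not brought into line with the 120 patients of 2.6 and 11.2, and primary completion at 36 months is not supported for the specificity outcome. Enrolment alone misses by about 4 months at the stated rate. With surveillance counted from enrolment, the last classification falls up to 24 to 28 months after the stated date (month 60 at 3.33 per month, month 64 at 3). The date could hold only if enrolment reached 3.33 per month and almost all late benign enrollees had histology or had begun surveillance about two years earlier. The 60-month study completion is marginal.

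This rests on uniform accrual, one rate for both groups and half the patients benign. The start of the two-year count and the share of benign patients with histology are not in the documents, so ranges are shown. The power statement and the choice of test are unaffected, provided that the calculation waits for all 60 benign patients.

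**What to change.** 1. Rewrite 11.3 for 120 patients, with an accrual rate that covers both groups.
2. State the date from which the two years of surveillance are counted.
3. Restate primary completion in 3.2.1 as the date when the last patient's reference status is due (up to about month 60 to 64 if counted from enrolment), or relabel 36 months as the end of accrual. Align 3.2.2 and 10.1 with it.
4. State in 10.1 that specificity is calculated once every patient has reference status under 2.6 and 11.1: histopathology, benign or malignant, or completed two-year surveillance. Report separately those who die or are lost without it.

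The 11.1 prediction-model rule should not be carried into 10.1 unchanged. It does not list benign histology, so read literally such patients would still wait two years, and it counts an undiagnosed death as complete although no reference status exists.

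The cost is amendment wording, amended registry dates and possibly a few more months of follow-up: 0 to about 4 beyond month 60 at 3.33 to 3 per month. The test and the sample size do not change.

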11.4. Criteria for future studies

If ¹⁸F-FSPG PET/CT imaging has a higher specificity for detecting malignant lung nodules compared to ¹⁸F-FDG PET/CT, a larger study will be planned.

